APPENDIX 3. GUIDELINES FOR EXPLORATORY BIOPSIES

This appendix provides timepoints and research exploratory biopsies of externally visible lesions in the office setting. These biopsies are performed during the screening period and on day 22 (± 3 days).

Research Procedures for ALL Biopsies:

Where and How:

The technique and sites of biopsies will be selected by the investigator based on the sizes and locations of lesions. Generally, biopsies will be punches of approximately 3mm diameter. In patients with nodal metastases and no residual primary, core needle biopsy may be performed. Biopsies should not be taken at the perimeter of a lesion because this could interfere with measurement of longest diameters for response assessments. Whenever possible, biopsy sites should be ≥ 5 mm from the edge of baseline lesional area if appropriate.

How many:

2 to 3 biopsies will be obtained at baseline and again at neoadjuvant treatment day 22 (± 3 business days). The first biopsy will be processed for FFPE, the second biopsy will be processed in RNAlater[®], and the third biopsy (if obtained) will be processed for FFPE.

11. Disposition of Samples

Biopsy samples required for exploratory assessments (baseline, neoadjuvant treatment day 22) will be provided to the sponsor. Further information is available in the laboratory manual.

APPENDIX 4. RESPONSE EVALUATION CRITERIA IN SOLID TUMORS: RECIST GUIDELINE (VERSION 1.1)

This appendix has been excerpted from the revised Response Evaluation Criteria in Solid Tumors (RECIST) guideline version 1.1 (Eisenhauer, 2009). For full details pertaining to the RECIST 1.1 criteria, please refer to the publication.

1. Assessment of Tumor Burden Measurable Disease at Baseline

Overall tumor burden must be assessed at baseline and will be used as comparator for subsequent measurements. Tumor lesions will be characterized as measurable or non-measurable as follows:

Response and progression will be evaluated in this study using the international criteria proposed by the revised Response Evaluation Criteria in Solid Tumors (RECIST) guideline (version 1.1; Eisenhauer, 2009). Changes in the largest diameter (unidimensional measurement) of the tumor lesions and the shortest diameter in the case of malignant lymph nodes are used in the RECIST criteria.

1.1. Measurable disease

Tumor lesions must be accurately measured in at least one dimension (longest diameter in the plane of measurement is to be recorded) with a minimum size of

- 10 mm by computed tomography (CT) scan (CT scan slice thickness no greater than 5 mm)
- 10 mm caliper measurement by clinical exam (lesions which cannot be accurately measured with calipers should be recorded as non-measurable)
- 20 mm by chest x-ray
- **Malignant lymph nodes:** To be considered pathologically enlarged and measurable, a lymph node must be ≥ 15 mm (≥ 1.5 cm) in short axis when assessed by CT scan (CT scan slice thickness recommended to be no greater than 5 mm [0.5 cm]). At baseline and in follow-up, only the short axis will be measured and followed.

1.2. Non-measurable disease

All other lesions, including small lesions (longest diameter < 10 mm or pathological lymph nodes with ≥ 10 to < 15 mm short axis), are considered non-measurable disease. Bone lesions, leptomeningeal disease, ascites, pleural/pericardial effusions, lymphangitis cutis/pulmonitis, inflammatory breast disease, and abdominal masses (not followed by CT, MRI, or PET) are considered as non-measurable.

1.2.1. Special Considerations

Bone lesions:

- Bone scan, PET scan or plain films are not considered adequate imaging techniques to measure bone lesions. However, these techniques can be used to confirm the presence or disappearance of bone lesions.
- Lytic bone lesions or mixed lytic-blastic lesions, with identifiable soft tissue components, that can be evaluated by cross sectional imaging techniques such as CT or MRI can be considered as measurable lesions if the soft tissue component meets the definition of measurability described above.
- Blastic bone lesions are non-measurable.

Cystic lesions:

Cystic lesions that meet the criteria for radiographically defined simple cysts should not be considered as malignant lesions (neither measurable nor non-measurable) since they are, by definition, simple cysts. “Cystic lesions” thought to represent cystic metastases can be considered as measurable lesions, if they meet the definition of measurability described above. However, if noncystic lesions are present in the same patient, these are preferred for selection as target lesions.

Lesions with prior local treatment:

- Tumor lesions situated in a previously irradiated area, or in an area subjected to other locoregional therapy, are usually not considered measurable unless there has been demonstrated progression in the lesion.

1.3. Methods of Assessment

All measurements must be recorded in metric notation, using calipers if clinically assessed. All baseline evaluations should be performed as closely as possible to the beginning of treatment and never more than 4 weeks before the beginning of the treatment.

The same method of assessment and the same technique should be used to characterize each identified and reported lesion at baseline and during follow-up. Imaging-based evaluation is preferred to evaluation by clinical examination unless the lesion(s) being followed cannot be imaged but are assessable by clinical exam.

- **CT and MRI.** CT is the best currently available and reproducible method to measure lesions selected for response assessment. This guideline has defined measurability of lesions on CT scan based on the assumption that CT slice thickness is 5 mm or less. When CT scans have slice thickness greater than 5 mm, the minimum size for a measurable lesion should be twice the slice thickness. MRI is also acceptable in certain situations (e.g., for body scans).

1.4. Baseline Documentation of Target and Non-Target Lesions

Target lesions: When more than one measurable lesion is present at baseline all lesions up to a maximum of five lesions total (and a maximum of two lesions per organ) representative of all involved organs should be identified as target lesions and will be recorded and measured at baseline. Target lesions should be selected on the basis of their size (lesions with the longest

diameter), be representative of all involved organs, and should lend themselves to reproducible repeated measurements.

Lymph nodes merit special mention since they are normal anatomical structures which may be visible by imaging even if not involved by tumor. Pathological nodes which are defined as measurable and may be identified as target lesions must meet the criterion of a short axis of ≥ 15 mm by CT scan. Only the short axis of these nodes will contribute to the baseline sum. All other pathological nodes (those with short axis ≥ 10 mm but < 15 mm) should be considered non-target lesions. Nodes that have a short axis < 10 mm are considered non-pathological and should not be recorded or followed.

A sum of the diameters (longest for non-nodal lesions, short axis for nodal lesions) for all target lesions will be calculated and reported as the baseline sum diameters. The baseline sum diameters will be used as reference to further characterize any objective tumor regression in the measurable dimension of the disease.

Non-target lesions: All other lesions (or sites of disease) including pathological lymph nodes should be identified as non-target lesions and should also be recorded at baseline. Measurements of these lesions are not required, but the presence, absence, or, in rare cases, unequivocal progression of each should be noted throughout follow-up. In addition, it is possible to record multiple non-target lesions involving the same organ as a single item on the case record form (e.g., ‘multiple enlarged pelvic lymph nodes’ or ‘multiple liver metastases’).

1.5. Response Criteria

This section provides the definitions of the criteria used to determine objective tumor response for target and non-target lesions.

1.5.1. Evaluation of Target Lesions

- **Complete Response (CR):** Disappearance of all target lesions. Any pathological lymph nodes (whether target or non-target) must have reduction in short axis to < 10 mm (< 1 cm).
- **Partial Response (PR):** At least a 30% decrease in the sum of the diameters of target lesions, taking as reference the baseline sum diameters.
- **Progressive Disease (PD):** At least a 20% increase in the sum of the diameters of target lesions, taking as reference the smallest sum on study (this includes the baseline sum if that is the smallest on study). In addition to the relative increase of 20%, the sum must also demonstrate an absolute increase of at least 5 mm (0.5 cm). (**Note:** the appearance of one or more new lesions is also considered progressions).
- **Stable Disease:** Neither sufficient shrinkage to qualify for PR nor sufficient increase to qualify for progressive disease, taking as reference the smallest sum diameters while on study.

Special notes on the assessment of target lesions:

- **Lymph nodes:** Lymph nodes identified as target lesions should always have the actual short axis measurement recorded and should be measured in the same anatomical plane as the baseline examination, even if the nodes regress to below 10 mm on study. This means that when lymph nodes are included as target lesions,

- the ‘sum’ of lesions may not be zero even if complete response criteria are met, since a normal lymph node is defined as having a short axis of <10 mm.
- Target lesions that become ‘too small to measure’: All lesions (nodal and non-nodal) recorded at baseline should have their actual measurements recorded at each subsequent evaluation, even when very small (e.g., 2 mm). If the radiologist is able to provide an actual measure, that should be recorded, even if it is below 5 mm. However, when such a lesion becomes difficult to assign an exact measure to then: (i) if it is the opinion of the radiologist that the lesion has likely disappeared, the measurement should be recorded as 0 mm. (ii) if the lesion is believed to be present and is faintly seen but too small to measure, a default value of 5 mm should be assigned (note: in case of a lymph node believed to be present and faintly seen but too small to measure, a default value of 5 mm should be assigned in this circumstance as well). This default value is derived from the 5 mm CT slice thickness (but should not be changed with varying CT slice thickness).
 - Lesions that split or coalesce on treatment: When non-nodal lesions ‘fragment’, the longest diameters of the fragmented portions should be added together to calculate the target lesion sum. Similarly, as lesions coalesce, a plane between them may be maintained that would aid in obtaining maximal diameter measurements of each individual lesion. If the lesions have coalesced such that they are no longer separable, the vector of the longest diameter in this instance should be the maximal longest diameter for the ‘coalesced lesion’.

1.5.2. Evaluation of Non-Target Lesions

While some non-target lesions may actually be measurable, they need not be measured and instead should be assessed only qualitatively at the time points specified in the protocol.

- **Complete Response:** Disappearance of all nontarget lesions and normalization of tumor marker level. All lymph nodes must be nonpathological in size (<10 mm short axis).
- **Non-CR/Non-PD:** Persistence of one or more nontarget lesion(s) and/or maintenance of tumor marker level above the normal limits.
- **Progressive Disease:** Appearance of one or more new lesions and/or unequivocal progression of existing nontarget lesions. Unequivocal progression should not normally trump target lesion status. It must be representative of overall disease status change, not a single lesion increase.

Although a clear progression of “nontarget” lesions only is exceptional, the opinion of the treating physician should prevail in such circumstances, and the progression status should be confirmed at a later time by the review panel (or investigator).

1.6. New Lesions

The appearance of new malignant lesions denotes disease progression; therefore, some comments on detection of new lesions are important. There are no specific criteria for the identification of new radiographic lesions; however, the finding of a new lesion should be unequivocal: ie, not attributable to differences in scanning technique, change in imaging modality or findings thought

to represent something other than tumor (for example, some ‘new’ bone lesions may be simply healing or flare of pre-existing lesions). This is particularly important when the patient’s baseline lesions show partial or complete response. For example, necrosis of a liver lesion may be reported on a CT scan report as a ‘new’ cystic lesion, which it is not.

A lesion identified on a follow-up study in an anatomical location that was not scanned at baseline is considered a new lesion and will indicate disease progression. An example of this is the patient who has visceral disease at baseline and while on study has a CT or MRI brain ordered which reveals metastases. The patient’s brain metastases are considered to be evidence of progressive disease even if he/she did not have brain imaging at baseline. If a new lesion is equivocal, for example because of its small size, continued therapy and follow-up evaluation will clarify if it represents truly new disease.

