In view of the high efficacy of cemiplimab against advanced CSCC and the positive phase 3 results among other anti-PD-1 antibodies in the adjuvant setting for melanoma patients, it is appropriate to evaluate cemiplimab in the post-operative setting. Therefore, Part 2 of this protocol allows adjuvant cemiplimab in patients who have not experienced disease progression or unacceptable toxicity during Part 1 (the neoadjuvant portion) of the study. An investigator, according to his or her clinical judgment, may opt to administer adjuvant radiation therapy in this study instead of adjuvant cemiplimab in Part 2. Such patients will not receive cemiplimab after this therapy but should be followed for disease recurrence and survival during the study. The data from Part 2 could inform the development of a future randomized trial to define adjuvant therapy for patients

with CSCC. However, the primary objective of this study is to assess neoadjuvant cemiplimab, not adjuvant therapy.

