9.2.2.4. Characterization of New Skin Lesions (Disease Recurrence) or SPT Following Surgery

In CSCC, the most common sites of metastases are lymph node and lung (Hillen, 2018). New CSCC lesions in the skin usually are not metastatic lesions. With rare exceptions, new CSCC lesions in the skin are new primary tumors due to field cancerization from chronic UV-mediated skin damage (Christensen, 2018). In a previous randomized trial in advanced CSCC, recurrent skin disease and SPTs were recognized as distinct entities (Brewster, 2007). In this study, SPTs are non-metastatic CSCC lesions in the skin that can be managed by local modality therapy as part of routine clinical practice.

However, there are 2 circumstances in which a new skin lesion in a CSCC patient could represent metastatic disease:

- Epidermotropic metastases (EDMs), defined as distant lesion(s) in the dermis without epidermal involvement (Skala, 2018)(Weidner, 1985). Although EDM are well described in the melanoma literature, this would be a highly atypical pattern of recurrence in patients with CSCC. However, EDM could occur in a CSCC patient because cutaneous metastases from squamous cancers arising in internal organs have been described (Bornkessel, 2006)(Plataniotis, 1999).

NOTE: In the event of a new rapidly growing CSCC lesion involving both dermis and epidermis that is not appropriate for local modality treatment and requires new systemic therapy, this should be designated as an EDM, not an SPT.

- In-transit metastases (ITMs) are defined as cutaneous nodule(s) distinct from the primary tumor and occurring proximal to the first lymph node basin (Xu, 2018). Of note, not all CSCC lesions arising in the skin proximal to the first lymph node basin are ITM. Due to chronic sun exposure, new lesions in sun-exposed skin may represent SPTs. The decision about whether to call such a lesion an SPT or an ITM will be based on the overall clinical presentation of the lesion. These ITMs are most often subcutaneous or dermal papules with occasional exophytic features (Carucci, 2004). The investigator will indicate in source documents and eCRF pages the basis for designating a new skin CSCC lesion as ITM or SPT.

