In this study, a new CSCC lesion arising on the skin during the study period will be classified as an SPT unless the lesion represents ITM or EDM. Second primary CSCC tumors are not counted as events for the DFS endpoint. Patients who develop ITM or EDM will be considered to have experienced a DFS event.

Second primary CSCC tumors arising during the study period should be treated with surgery or another permitted local modality. Permitted non-surgical local modalities for SPTs in this study are: topical 5-fluorouracil, topical imiquimod, and photodynamic therapy with topical aminolevulinic acid or methyl aminolevulinate (Christensen, 2018).

For any cutaneous lesion that is resected during the course of the study, the following information will be captured in eCRF pages: histologic diagnosis, maximum diameter, and investigator's impression regarding whether lesion represents SPT or a disease recurrence (either ITM or EDM). The reason the investigator deems a lesion to be SPT or recurrence will be documented in eCRF.

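### No rule says a second primary skin CSCC in Part 1 is not a RECIST new lesion, so it may be coded as progression and stop cemiplimab after 2 of 4 doses

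*Protocol*

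**What the plan says.** **RECIST rule.** Protocol Appendix 4, section 1.6, states: "The appearance of new malignant lesions denotes disease progression". Section 1.5.1 repeats this in its note on progressive disease. The table in section 1.7 scores any unequivocal new lesion as PD, whatever the target lesions do. The carve-outs in 1.6 are for findings that are not tumor and for equivocal lesions.

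**Consequences in Part 1.** Section 8.3.1 lists progression as a reason for permanent discontinuation. Section 8.3.5 defines that progression by RECIST 1.1 and Appendix 4 and sends the patient to surgery. Section 9.1.5.1 makes patients who discontinue for this reason ineligible for adjuvant cemiplimab. Section 6.1.2 requires the first response scan (day 35 through 46) before dose 3.

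**Second primary tumors.** Section 9.2.2.4 says: "With rare exceptions, new CSCC lesions in the skin are new primary tumors due to field cancerization". It also says that "a new CSCC lesion arising on the skin during the study period will be classified as an SPT", unless it is an in-transit (ITM) or epidermotropic (EDM) metastasis. The one endpoint exemption it states is: "Second primary CSCC tumors are not counted as events for the DFS endpoint". The section heading limits it to the period following surgery.

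**ORR.** Protocol 5.2.1 and SAP 4.4.2 use investigator-assessed RECIST 1.1 without confirmation. The SAP has no rule for SPTs.

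**The concern.** The protocol describes an SPT as non-metastatic and manageable with local treatment, and expects almost every new skin CSCC to be one. Section 3.3.2 justifies early diversion to surgery by the danger that the tumor progresses and curative resection is lost. A separate, locally treatable skin primary does not carry that danger. A patient whose index tumor is responding could nevertheless lose half of the neoadjuvant course and the adjuvant option because of it.

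Sites may also code the same lesion differently, some following Appendix 4 and some following 9.2.2.4. That adds noise to ORR, and each PD call that precedes a recorded response lowers it.

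**Working it through.** The plan gives no figure on this point, so the check is mainly a trace of the rules.

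**Step 1. Is a Part 1 SPT a new lesion under Appendix 4?** A histologically confirmed CSCC is malignant and is not equivocal, so neither carve-out in 1.6 applies. Sections 1.5.1, 1.6 and 1.7 then all give PD.

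**Step 2. Does another section override this?** Section 9.2.2.4 is the only candidate. Its heading says after surgery, while its classification sentence covers the whole study period. Even on the wider reading, the sentence assigns a class and the section removes that class from DFS only. Nothing links it to RECIST PD, to 8.3.1 or to ORR.

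**Step 3. What follows from PD at the day 35 to 46 scan?**
- Doses already given: 2 (days 1 and 22). Planned neoadjuvant doses: 4. Lost: 4 − 2 = 2 (8.3.1).
- Surgery is brought forward (8.3.5).
- Adjuvant cemiplimab, optional and up to 16 doses (6.1.3), is barred (9.1.5.1).

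**Step 4. What follows from PD at the pre-surgery scan?** All 4 doses can already have been given, so no neoadjuvant dose need be lost. Section 9.1.5.1 covers patients who discontinue drug and does not clearly apply.

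**Step 5. When is an ORR response lost?** Best overall response is the best one recorded on treatment (Appendix 4, 1.7), and confirmation is not required.
- SPT present at the first scan, no CR or PR recorded earlier: that scan is PD however far the target lesions have shrunk, and the patient is a non-responder.
- PR at the first scan, SPT first seen at the pre-surgery scan: best response stays PR and nothing is lost.

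**Step 6. Size per patient.** With 76 patients in the analysis set, one lost responder is 1/76 = 0.0132, or 1.3 percentage points. For scale, protocol Table 6 gives an exact 95% interval of 0.321 to 0.553 for 33 of 76, a width of 0.553 − 0.321 = 0.232, or 23.2 points.

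**Step 7. Other endpoints.**
- pCR is read from the surgical specimen (5.2.1), so an SPT can affect it only by shortening treatment. Two doses still leave a chance of pCR: Section 3.2.2 reports a clinically meaningful pCR rate in the pilot study after two doses.
- EFS counts pre-surgical progression only when it precludes surgery (5.2.1), so a resectable SPT is not an event.
- The sample size of 72, raised to 76, does not depend on any of this.

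**The case against.** The strongest reply is that 9.2.2.4 is study-specific text on exactly this lesion and Appendix 4 is a generic excerpt. The classification sentence covers the study period and the section directs local treatment, so an investigator can reasonably decline to call PD. This stands as far as it goes. A reader might infer that the protocol positively rules every Part 1 SPT to be PD; the documents do not support that. They leave two readings open, and the literal one withdraws drug.

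A reader might also infer that DFS is the only endpoint that spares an SPT. EFS spares a resectable one too.

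A third tempting reading is that PD at the pre-surgery scan also bars Part 2 drug. Section 3.2.3 says "Part 2 of this protocol allows adjuvant cemiplimab in patients who have not experienced disease progression or unacceptable toxicity during Part 1", but that is a rationale section, and the operative Section 6.1.3 states no such bar.

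The route is also narrow. To cost neoadjuvant doses, a new skin CSCC must appear within about six weeks, be unequivocal and be called PD despite 9.2.2.4. Radiology is the primary assessment method, and 1.6 allows treatment to continue for an equivocal lesion. ORR is a secondary endpoint reported with a confidence interval and no test.

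Finally, counting any new malignant lesion as PD is conservative in an open-label, single-arm trial with investigator-read response. That is a fair argument for keeping such a count as a sensitivity analysis. It does not justify withdrawing treatment.

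**Conclusion.** The point holds as a gap between two sections. Read literally, Appendix 4 makes a Part 1 SPT progression, and no sentence prevents that reading. The main consequence is for treatment: a PD call at the day 35 to 46 scan leaves the patient with 2 of 4 neoadjuvant doses, early surgery and no adjuvant cemiplimab.

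The effect on ORR is 1.3 points per affected responder, assuming all 76 patients are in the analysis set and no CR or PR was recorded before the SPT. A reader might infer a material bias in ORR. The documents give no SPT rate, so no total can be derived; given the conditions needed, it is probably small. The primary analysis is touched only through fewer doses. This is worth correcting because the change is cheap, not because the trial's conclusions are at risk.

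**What to change.** 1. **Endpoint.** State in Appendix 4 section 1.6 and in SAP 4.4.2 that a histologically confirmed new skin CSCC meeting the 9.2.2.4 definition of an SPT (not ITM or EDM) is recorded as an SPT and is not a RECIST new lesion in Part 1.
2. **Treatment.** State in protocol 8.3.1, 8.3.5 and 9.1.5.1 that an SPT alone does not require stopping cemiplimab or early surgery and does not bar Part 2 cemiplimab.
3. **Reporting.** List all Part 1 SPTs and report ORR with each counted as PD in a sensitivity row.

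**Cost.** Wording in five places, one listing and one table row. The sample size and the primary analysis do not change.

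**Downside.** An unblinded investigator separates SPT from metastasis. For in-transit lesions, 9.2.2.4 says the decision "will be based on the overall clinical presentation of the lesion". Histology showing CSCC does not settle the question alone, so ORR could be biased upward. The reason for the classification, which 9.2.2.4 already requires in the eCRF, and the sensitivity row limit this.
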